Aim 2: For this aim, we will compare objective measures of image quality including signal to noise ratio using dynamic Rubidium-82 or N-13 ammonia images, the frequency of misregistration between PET and CT, the frequency of presumed motion artifact and bowel radiotracer activity. These measures will be compared using a student's t-test or a Pearson Chi square test, as appropriate. A P-value of <0.05 will be considered significant.

Aim 3: For this aim, we seek to compare measures of semi quantitative relative perfusion, absolute perfusion and LVEF using the Lexiscan alone compared to Lexercise PET. Firstly, we will compare semi-quantitative defect size, severity and reversibility between the Lexercise and Lexiscan PET studies. Based on the results of one prior study using N-13 ammonia and comparing dipyridamole versus treadmill exercise², a sample size of 24 subjects with reversible defects should be adequate to identify if significant differences exist between Lexercise and Lexiscan PET protocols. Next, we will compare the differences in regional rest and peak stress myocardial blood flow and coronary flow reserve in the defect territory compared to normal territory between the Lexercise and Lexiscan protocols. Finally, we will study the changes in LVEF from rest to peak stress in Lexercise versus Lexiscan PET studies in the normal and ischemic subjects.

[figure not shown]
I. BACKGROUND:

Myocardial perfusion imaging (MPI) with positron emission tomography (PET) is more accurate than single photon emission computed tomography (SPECT)³, enables non-invasive quantitation of absolute myocardial blood flow (MBF), and is particularly helpful in the obese individuals and those that are unable to exercise.³ Presently PETMPI is indicated only for subjects that are unable to exercise⁴,

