Hypothesis 1: Lexiscan will cause further/maximal vasodilation in a subject that is already vasodilated from exercise; therefore, the safety of this protocol needs to be ascertained. Lexiscan is expected to be well tolerated when injected during maximal exercise stress without any increase in major adverse events.

Aim 2: To **assess the image quality** of Lexercise PET compared to Lexiscan.

Hypothesis 2: Image quality as assessed by myocardial count density and heart to liver ratio will be superior with Lexercise compared to Lexiscan. However, misregistration artifacts from upward diaphragmatic creep will be higher with Lexercise compared to Lexiscan.

Aim 3: To compare **relative and absolute PET** with Lexercise compared to Lexiscan PET in identifying CAD.

Hypothesis 3: Lexercise PET offers the advantage of imaging reduced myocardial blood flow from vasoconstriction in diseased territories and maximal vasodilation in normal territories. Therefore, in patients with ischemic scans, the defect contrast on relative will be better with Lexercise compared to Lexiscan PET. We hypothesize that the differences in regional CFR between normal and abnormal territories will be greater with Lexercise compared to Lexiscan.

Significance of the mechanistic questions of this proposal:

The overall goal of this proposal is to evaluate the feasibility, utility and mechanistic underpinnings of a novel protocol incorporating combined maximal symptom limited exercise treadmill test with Lexiscan compared to Lexiscan alone. The combined standard symptom limited exercise stress testing with Lexiscan has several novel clinical and research applications:

1. This protocol provides exercise data (hemodynamic, electrocardiographic and clinical data) combined with high quality PET imaging that is important in patient management.
2. A PET MPI study can be performed with physiological exercise stress using any of the available flow tracers (Rubidium-82, N-13 ammonia, or the new compound BMS747158, an F-18 labeled agent) with minimal radiation exposure to the staff.
3. This protocol makes it feasible to assess both endothelium dependent (exercise) and endothelium independent (Lexiscan) mechanisms affecting MBF.

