- Sub diaphragmatic activity (liver heart ratios)
- Defect contrast
- Signal to noise ratio and
- Dynamic image evaluability will be assessed

VI. BIOSTATISTICAL ANALYSIS

The overall aim of this pilot study of 50 patients is to assess the tolerability, safety, diagnostic accuracy and image quality between Lexiscan with symptom limited exercise compared to Lexiscan alone.

Aim 1. For this aim, we will compare the reported side effect profile for Lexercise to Lexiscan PET, using a Pearson Chi square test. A P-value of <0.05 will be considered significant.

Aim 2: For this aim, we will compare objective measures of image quality including signal to noise ratio using dynamic Rubidium-82 images or N-13 ammonia, the frequency of misregistration between PET and CT, the frequency of presumed motion artifact and bowel radiotracer activity. These measures will be compared using a student's t-test or a Pearson Chi square test, as appropriate. A P-value of <0.05 will be considered significant.

Aim 3: For this aim, we seek to compare measures of semi quantitative relative perfusion, absolute perfusion and LVEF using the Lexiscan alone compared to Lexercise PET. Firstly, we will compare semi-quantitative defect size, severity and reversibility between the Lexercise and Lexiscan PET studies. Based on the results of one prior study using N-13 ammonia and comparing dipyridamole versus treadmill exercise², a sample size of 35 subjects with reversible defects should be adequate to identify if significant differences exist between Lexercise and Lexiscan PET protocols. Next, we will study the changes in LVEF from rest to peak stress in Lexercise versus Lexiscan PET studies in the normal and ischemic subjects. Finally, we will compare regional rest and peak stress myocardial blood flow and coronary flow reserve between Lexercise and Lexiscan PET studies.

VII. RISKS AND DISCOMFORT

Time: Participation in this trial entails an exercise vasodilator stress Rubidium-82 PET or N-13 ammonia scan. The total time spent for the study procedures is approximately 1 hour.

Intravenous line insertion: Possible side effects intravenous line insertion are pain, bruising, or infection where the needle entered the skin. Some people faint or get dizzy during insertion of the intravenous line.

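### Section VI specifies no test of Hypothesis 3 under Aim 3: it omits the Synopsis's defect-versus-normal territory comparison, and defect contrast is neither defined nor analysed

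*Combined protocol and SAP*

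**What the plan says.** Hypothesis 3 (Section II, Specific Aims) makes two predictions. For patients with ischemic scans, "the defect contrast on relative will be better with Lexercise compared to Lexiscan PET". For absolute flow, "the differences in regional CFR between normal and abnormal territories will be greater with Lexercise compared to Lexiscan".

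Two current texts describe the Aim 3 analysis.

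- **Synopsis, Statistical Plan.** After the semi-quantitative defect measures, it compares rest flow, stress flow and "coronary flow reserve in the defect territory compared to normal territory between the Lexercise and Lexiscan protocols".
- **Section VI, Biostatistical Analysis.** It begins "Firstly, we will compare semi-quantitative defect size, severity and reversibility between the Lexercise and Lexiscan PET studies", moves to the change in LVEF, and ends "Finally, we will compare regional rest and peak stress myocardial blood flow and coronary flow reserve between Lexercise and Lexiscan PET studies". It mentions neither defect nor normal territory.

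The endpoint list at the end of Section V names defect contrast twice: under diagnostic value, as a comparison between protocols, and under image quality. Section V defines the summed scores and percent myocardium but not contrast. Neither Aim 3 text names contrast, and the Aim 2 analysis does not name it either.

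Section V does plan flow and CFR for each of three vascular beds, and assigns perfusion defects to vascular distributions.

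**The concern.** The rationale for Lexercise is selective. Normal arteries should dilate further at peak exercise while diseased ones should hardly respond. That is a statement about how the protocol effect differs between territories within a patient. Section VI's last sentence looks only at the protocol effect within a region.

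An analyst working from Section VI could therefore report a significant CFR change with Lexercise that is the same in healthy and diseased territory, and have it read as support for Hypothesis 3. The reverse is also possible: higher CFR in the defect territory could be read as less disease while the gap to normal had widened. The other half of the hypothesis, defect contrast, could be left unanalysed or be defined after the images have been seen.

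**Working it through.** **1. The plan's own figures.** The Synopsis gives 24 subjects with reversible defects and Section VI gives 35, both said to rest on a prior N-13 ammonia study. (Both cite reference 2, the Rubidium-82 study; the N-13 study is reference 8, and its Table 3 is used here.) Endpoint, test, sidedness and power are not stated. Assume a paired t-test, two-sided 0.05, 80% power, with SD of the paired difference = √(s₁² + s₂² − 2·r·s₁·s₂).

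- Summed stress score: √(5.7² + 5.9² − 2·0.80·5.7·5.9) = 3.673; 2.2/3.673 = 0.599; n = 24.
- Summed difference score: √(4.7² + 4.6² − 2·0.61·4.7·4.6) = 4.108; 2.1/4.108 = 0.511; n = 33.
- Stress defect size: √(11.5² + 13.6² − 2·0.62·11.5·13.6) = 11.103; 5.5/11.103 = 0.495; n = 34.

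So 24 can be matched exactly and 35 to within 2, under these assumptions, and in each case from a semi-quantitative defect measure. Neither number is built on a Hypothesis 3 measure.

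**2. The texts side by side.**

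| Measure | Hypothesis 3 | Endpoint list | Synopsis, Aim 3 | Section VI, Aim 3 |
|---|---|---|---|---|
| Defect contrast | yes | yes, undefined | no | no |
| Normal versus defect territory CFR | yes | no | yes | no |
| Flow and CFR between protocols | no | yes | only within the territory comparison | yes, regional |

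**3. Why the third row does not stand in for the second.** Let N and D be CFR in normal and defect territory, with E for Lexercise and L for Lexiscan. Section VI estimates N_E − N_L and D_E − D_L separately. Hypothesis 3 concerns Δ = (N_E − D_E) − (N_L − D_L) = (N_E − N_L) − (D_E − D_L). If both territories change by the same amount c, each regional comparison shows c and Δ = 0. If regions are taken as the three vascular beds without labelling, each bed also pools patients in whom it is diseased with patients in whom it is normal.

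**4. Size of the mismatch.** Suppose CFR shifts equally in all territories by 0.5 SD of the paired change (assumed), so Δ = 0. The probability that a paired t-test on one region gives p < 0.05 is:

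| Pairs | 19 | 24 | 29 | 35 |
|---|---|---|---|---|
| Probability | 0.54 | 0.65 | 0.74 | 0.82 |

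Here 19 = 24 − 5 (Synopsis) and 29 = 34 − 5 (Section III), after removing the 5 ischemic subjects sent to repeat Lexiscan. 24 and 35 are the stated sample sizes.

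**5. Scale.** Take assumed Lexiscan CFRs of 3.0 (normal) and 1.5 (defect), so the gap is 1.5 and the defect/normal ratio is 0.50.

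- Proportional rise of 10–30%: normal 3.30–3.90, defect 1.65–1.95, gap 1.65–1.95, ratio 0.50.
- Equal rise of 0.5: normal 3.5, defect 2.0, gap 1.5, ratio 2.0/3.5 = 0.57.

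The gap moves under the first and the ratio under the second, so neither scale is neutral and the two are informative together.

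**6. Precision of the missing comparison.** The documents give no SD or expected effect for Δ or for defect contrast, so no required n can be computed. The smallest paired effect detectable with 80% power, two-sided 0.05, is 0.68 SD (n = 19), 0.60 (24), 0.54 (29) and 0.49 (35). If the protocol change within a territory has SD s = 0.4–0.8 CFR units and the between-territory correlation ρ is 0–0.7 (assumed), then SD(Δ) = s·√(2(1 − ρ)) runs from 0.31 to 1.13. The detectable Δ is then 0.21–0.77 CFR units at n = 19 and 0.15–0.55 at n = 35.

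**The case against.** The strongest reply is that the protocol is a single document whose Synopsis already specifies the territory comparison, that contrast is a declared endpoint compared between protocols, and that the per-bed data needed for both are planned. All of this is correct, and it limits the point to a conflict between two texts plus an endpoint without a definition or analysis.

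Three stronger readings are tempting, and the documents do not support them.

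- A reader might infer that the plan cannot answer Aim 3. Aim 3 is broader than Hypothesis 3: it concerns relative and absolute PET "with Lexercise compared to Lexiscan PET in identifying CAD". The defect measures, LVEF and regional flow in Section VI all bear on it.
- A reader might infer that a wider gap caused by a proportional rise leaves Hypothesis 3 untested. The hypothesis is worded as a difference, so a wider gap is what it predicts. Whether the gap is selective is a further question.
- A reader might infer that the ratio should lead and defect size become descriptive. That preference rests on an assumed proportional rise; an equal rise reverses the picture (step 5). The only sample-size statement is also tied to the defect measures.

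It is also fair to say that defect severity overlaps with contrast, and that Section VI's regional comparison would report normal as well as diseased territory. What survives is that reporting two regional changes is not a test of whether they differ.

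**Conclusion.** The point holds for Section VI, not for the document as a whole. Section VI specifies no test of Hypothesis 3. The territory comparison stands only in the Synopsis, and defect contrast has no definition or named analysis in either Aim 3 text. This rests on reading alone and is firm.

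The false-signal probabilities of 0.54 to 0.82 depend on the assumed uniform 0.5 SD shift; they show what the Section VI comparison would respond to and do not forecast this trial. The CFR values in step 5 and the SD and correlation ranges in step 6 are likewise assumptions, because the documents report no CFR data. The conflict should be resolved before analysis, since it decides which result is reported as the test of the hypothesis.

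**What to change.** Reconcile the two Aim 3 texts as follows.

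1. Replace the last sentence of Section VI, Aim 3 with the Synopsis comparison, as a within-patient paired analysis in ischemic patients who have both a Lexiscan and a Lexercise scan. For each scan compute normal-territory minus defect-territory CFR, and the same for stress flow, using the same territories on both scans. Compare protocols on that difference.
2. Report the defect/normal ratio as a supporting analysis, to show whether a wider gap is selective or only proportional.
3. Define defect contrast as defect counts divided by normal-territory counts on the same static image (a lower value means a stronger contrast), and compare it between protocols in pairs.
4. State the paired test and alpha, which Aim 3 currently lacks, and how two defect territories in one patient are combined.
5. Keep defect size, severity and reversibility as planned.

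The cost is wording and some analysis of images and per-bed values already planned. Patients with defects in all three territories have no normal reference and drop out of this measure. The 5 ischemic patients assigned to repeat Lexiscan do not contribute, which leaves at most 19 pairs (Synopsis counts) or 29 (Section III counts). Report the number of usable pairs, and state that the sample size was not set for these measures.
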